To assess the effectiveness of this multilevel intervention, called the workplace *Metabolic Health Improvement Program (MHIP)*, we will conduct a double-randomized trial in partnership with the clinical trials division of a large Northern California-based academic healthcare system, Sutter Health ($N=700$ employees on $N=16$ hospital campuses). We will first cluster-randomize 8 Sutter Health hospital campuses to the SSB sales ban condition and 8 campuses to serve as controls (no sales ban). Across these 16 campuses, we will further randomize heavy-SSB-consuming employees (>30 oz/week) to receive a brief SSB counseling intervention delivered remotely or to a control condition.^{11,12} The **primary outcomes** are central obesity (e.g., waist circumference) and change in serum insulin sensitivity (homeostatic model assessment [HOMA] ratio). **Secondary outcomes** include changes in SSB consumption, Body Mass Index (BMI), and lab values to include: lipid profile, triglycerides, triglyceride:HDL ratio, uric acid, ApoA, ApoB, lactate, ALT/AST, GGT, fasting glucose, fasting insulin, HbA1c. We will assess dietary composition remotely using the Automated Self-Administered 24-hour (ASA-24) at baseline, 6 and 12 months, and waist circumference remotely with empirically validated instructions and a standardized tape measure provided to participants. We will collect blood samples in the workplace labs at baseline and 12 months. All analyses will consider compensatory changes in at-home SSB intake, calories from sugar, and total calories. Aims are:

Aim 1: How well does each intervention work alone? We will assess the independent effects of the brief counseling intervention and workplace SSB sales ban on changes in primary and secondary outcomes. We will compare outcomes across employees exposed to the brief intervention only ($n=175$), SSB sales ban only ($n=175$), and no intervention ($n=175$). *We hypothesize that the brief counseling intervention and sales ban will each independently decrease waist circumference and HOMA relative to no intervention. Those at high risk (baseline BMI >25 , ethnic-minority, and lower-occupational status) will benefit more from the interventions.*

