analyses will contribute new knowledge by testing the effectiveness of sales bans using anthropometrics and blood biomarkers in the first fully-powered randomized controlled trial.

Our preliminary studies suggest that brief SSB counseling interventions and workplace sales bans could be potentially synergistic with respects to obesity prevention: The proposed trial leverages multiple levels of the socioecological model in mutually-reinforcing ways.⁶³ While the sales ban intends to reduce availability, and the environmental cues associated with SSBs in the workplace, the brief intervention provides employees with a motivational boost to cut down or quit. In our UCSF pilot study of heavy SSB drinkers, all were exposed to a sales ban and half were randomized to a brief motivational counseling intervention. We found that the combined effects led to reductions in SSB consumption of 24 oz/day compared to an 8 oz/day reduction for employees exposed to the sales ban alone (see “Preliminary Studies”).^{11,12} This pilot study, however, was not fully powered or able to test the brief intervention in the absence of a sales ban. *Under Aim 2, we will pursue the hypothesis that reduced SSB availability and cues under a sales ban, combined with the motivational boost of a brief intervention, will optimize outcomes.*

Exploring mechanisms of change. The NIH Common Fund is spearheading the Science of Behavior Change (SoBC) Initiative to urge scientists to explore the mechanisms of action in behavior change interventions, thus promoting the cumulative advancement of science.⁶⁴ The SoBC model (see Figure 2 below) allows scientists to systematically explore the “how and why” behind changes in obesogenic behaviors, thus contributing to the development of blueprints for more effective obesity prevention. Our pilot study found that employees who reported drinking SSBs due to strong cravings did not benefit from the sales ban alone.¹² But if those who received the brief intervention reduced their consumption by over 19 oz/day. SSB cravings could, therefore, be a mechanism on the critical pathway leading from the multilevel intervention to changes in central obesity (see “Preliminary Studies”). *If the multilevel intervention proves to be effective, mediation analyses proposed under Aim 3 will help shed light on why. If not effective, they will help us to build future interventions that are more effective.*

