Public health impact: If effective, the proposed employer-sponsored multilevel intervention will offer an efficient, scalable strategy for preventing obesity in millions of American working adults. This study will also contribute to science on mechanisms of change in obesity prevention and inform the design of interventions that exploit synergies between individual behavior change strategies and food environment policies.

4. METHODS:

(4a) General Study Design:

This is a prospective, double-randomized study in which 16-Sutter Health affiliate hospital campuses will be cluster randomized to control (no SSB sales ban) vs. intervention (removal of SSBs). Across these 16 campuses, we will enroll 700 employees and then randomize those who self-report consuming >30 oz of SSB per week to receive a brief counseling intervention or control (no intervention).

**SUTTER HEALTH
INSTITUTIONAL REVIEW BOARD**

Protocol Summary Form

(4b) Procedures:

Cluster Randomization of 16 Sutter Health Affiliates

Sutter Health affiliates will be eligible to participate in the study who meet the criteria: 1) the affiliate has not participated in a SSB intervention; 2) the affiliate is not in a county that has instituted a SSB sales tax. Affiliates will be stratified by their location (urban vs. rural) and number of employees and will be randomly assigned using a computer program to be assigned to either control or intervention. Sutter Health leadership ([name] and [name]) have signed a letter of support to conduct this study.

Sites randomized to the SSB will eliminate sugar-sweetened beverages from the cafeterias, vending machines, Walgreens, vendors, and from patient care areas. Sutter Health has already implemented Healthy Beverage Initiatives (HBI) at Alta Bates, Palo Alto Medical Foundation (PAMF) and all CPMC campuses.

Study Procedure	Description	Baseline	6 Months	12 Months
Informed Consent	Procedures Described Below	X		
Demographics	Self-reported gender, ethnicity, household income, education, work location, hours, shifts	X	X	X
Medical History	Self-reported concurrent medications and general medical history with an emphasis on diabetes	X	X	X
Height	Measured using a stadiometer on a standardized scale at a semi-private location on the affiliate campus.	X		
Weight	Obtained on a standardized scale at a semi-private location on the affiliate campus.	X	X	X

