Analytic Plan: We will analyze Aim 1 using all data collected at the baseline, 6- and 12-month time points. First, we will use ANOVA to compare group means and determine whether there is a significant main effect for each intervention (the sales ban and the brief intervention). Based on theory and our previous studies, we know that baseline risk factors and demographics are likely relevant to the impact of these interventions; those at greater baseline risk tend to benefit more from the interventions. Therefore, each dependent variable will also be examined using a linear regression model, which allows us to observe the main effects of these factors. For example, the model predicting HOMA change would include assignment to the sales ban condition (coded as 0/1), assignment to the brief intervention condition (coded as 0/1), baseline HOMA, baseline SSB consumption, baseline BMI, race/ethnicity, and sex. Subsequent models can consider baseline BMI > 25, ethnicity and job classification. The procedure for analyzing each outcome would be the same, but with each primary and secondary outcome substituted for HOMA in turn.

For SSB consumption, we will examine at-work consumption, at-home consumption, and total consumption as separate outcomes to thoroughly investigate the impact of the interventions across work and home environments. We will similarly check for potential compensatory consumption in sugar from calories and total calories for participants in the intervention conditions relative to controls. If ASA-24-based total calories or calories from sugar disproportionately increase in the intervention groups, this suggests a compensatory effect.

Although we believe our strategy of cluster randomization and controlling for individual differences that can vary regionally (such as ethnic distribution) is sufficient, we will also analyze the effects of the brief intervention via an exploratory mixed regression model, with individuals nested within sites, to see if study site was an important factor. If it is, we will consider mixed models where possible.

**SUTTER HEALTH
INSTITUTIONAL REVIEW BOARD**

Protocol Summary Form

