Power Calculations: Power calculations are based on changes observed in the pilot study and response rates from the current Sutter Health trial. Calculations are conservative, based on 80% retention of participants after 12 months. With an initial N of 700 drawn from 16 Sutter Health sites randomly assigned to the sales ban and control conditions, and with participants within those sites randomly assigned to brief intervention/no brief intervention conditions, 80% retention would result in an overall N of 550 at 12 months. This results in approximately 138 in each of four experimental conditions: brief intervention + sales ban, the brief intervention only, sales ban only, and no intervention. Power analysis for a full factorial design conducted with the BDEsize¹⁰⁹ package within R¹¹⁰ indicates that with 80% power and an alpha level of .05, we will be able to detect effect sizes as small as .08 for the effect of each intervention on each outcome.

Anticipated Problems and Alternative Approaches: One potential problem is attrition, particularly biased attrition. We have calculated the sample to allow for up to 20% attrition; this is a conservative number based on our current Sutter Health data. In the UCSF pilot, which took place entirely pre-pandemic, we achieved a 94.4% response rate for blood draws. The existing study team has experience with the challenges of retaining a sample of health care workers during a challenging time and can use the same techniques (e.g., email and phone outreach) to reduce attrition here. We will conduct statistical tests to determine if attrition is biased on baseline risk levels, demographic factors (including regional differences), or study condition.

As with all self-report data, the survey data on SSB consumption could be biased, perhaps particularly for intervention participants who want to self-present improvement. However, the anthropometric and blood measures are objective and should show a consistent pattern with the SSB changes. Standard data cleaning procedures should reveal any extreme cases of self-representation bias. For SSB consumption data, we have also established a convention in previous studies of pruning outliers that are more than 4 SD away from the mean to reduce error from participants who may have responded inaccurately.

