Analytic Plan for Aim 2: Having established the main effects of each intervention under Aim 1, our analyses for Aim 2 focus on the interaction between them. Specifically, we anticipate that the combined intervention will have an effect above and beyond the simple additive effects of the two interventions. This analysis will require replicating the ANOVA and regression models used for Aim 1 with the addition to each of an interaction term for the two interventions. For example, the model predicting HOMA change will include assignment to the sales ban condition (coded as 0/1), assignment to the brief intervention condition (coded as 0/1), the interaction term for the two conditions (sales ban*brief intervention), baseline HOMA, baseline SSB consumption, baseline BMI, race/ethnicity, job classification (if sample size allows, as above), and sex. The procedure for analyzing each outcome is the same, but with each primary and secondary outcome substituted for HOMA in turn. This time, the main variable of interest will be the interaction term. We will graph and deconstruct each significant interaction term to determine the details of the interaction.

Power Calculations: As with Aim 1 above, power calculations are based on findings from the UCSF pilot and retention rates from the Sutter pilot. We will have 175 participants in each of the following groups. With 80% retention, this allows a final N of 550, with approximately 138 in each of the four experimental conditions. Power analysis for a full factorial design conducted with the BDEsize¹⁰⁹ package within R¹¹⁰ indicates that at 80% power and an alpha level of .05 we will be able to detect effect sizes as small as .12 for the interaction between the two interventions.

Anticipated Problems and Alternative Approaches: As with Aim 1, attrition and self-report bias are the primary potential issues we anticipate; handling of each is described above.

Expected Outcomes: We anticipate a significant interaction term, and more specifically, that the effect of the sales ban and brief intervention together will be stronger than each is individually. Participants assigned to the brief intervention and working at sites with a sales ban would thus demonstrate the greatest amount of change, and more change than one would expect if the effect of the two conditions were simply additive.

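### One smallest detectable effect (.08, scale not named) is given for both interventions without any clustering term, but the campus-randomised sales ban needs its own, larger figure than counselling

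*Combined protocol and SAP*

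**What the plan says.** Section 1 sets out two levels of randomisation. For the ban, "We will first cluster-randomize 8 Sutter Health hospital campuses to the SSB sales ban condition and 8 campuses to serve as controls". Counselling is assigned to individuals, stratified by location (Section 4b, Participant Randomization).

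Section 4c, Aim 1, Power Calculations starts from 700 employees at 16 sites, takes 550 at 12 months (about 138 per cell), and concludes: "we will be able to detect effect sizes as small as .08 for the effect of each intervention on each outcome". Aim 2 uses the same N and method: "we will be able to detect effect sizes as small as .12 for the interaction between the two interventions". Neither paragraph names the effect-size scale or mentions an ICC, design effect or campus-level degrees of freedom.

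The Aim 1 Analytic Plan relies on ANOVA and linear regression with no site term. It adds that "we will also analyze the effects of the brief intervention via an exploratory mixed regression model, with individuals nested within sites", to see whether site matters, and then: "If it is, we will consider mixed models where possible". Section 3 describes the Aim 1 contribution as "testing the effectiveness of sales bans using anthropometrics and blood biomarkers in the first fully-powered randomized controlled trial".

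**The concern.** A factor randomised to 16 campuses is estimated from differences between campuses. Its standard error therefore includes between-campus variation, and its valid test has 16 − 2 = 14 degrees of freedom. A factor randomised to individuals within campuses avoids both penalties. One detectable effect for both treats 550 employees as 550 independent units for the ban.

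The unnamed scale adds to the problem. A value of .08 could be a standardised difference d, Cohen's f, f-squared, eta-squared or a scale particular to the software, and these differ several-fold in SD units.

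The ban is half of Aim 1, and these two paragraphs hold the only power figures in the documents. A reader cannot see that the ban comparison is the less sensitive one, and a null ban result could be taken as coming from an adequately powered test.

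**Working it through.** **Inputs.** From Section 4c: N = 550, four cells, alpha .05 (two-sided assumed, as sidedness is not stated), power 80%. From Section 1: 16 campuses, 8 v 8. Campus size m = 550/16 = 34.4, taken as equal. ICC: not in the documents; assumed 0, .01, .02 and .05.

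**1. The plan's own figures.** For a 1-df effect in a 2×2 design with independent observations, use the noncentral F with df 1 and 546 and noncentrality 550·f². Solving for 80% power:

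- f = .1197, so d = 2f = 0.239 SD; f² = .0143; eta² = .0141.
- Interaction: also f = .1197, a difference-in-differences of 4f = 0.479 SD.

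The printed .08 is not reproduced as d, f, f² or eta². It does appear on a four-cell scale, the root of the summed squared effects divided by four:

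- Main effect (two levels of ±d/2): √(2 × .1197² / 4) = .0846.
- Interaction (four cells of ±f): √(4 × .1197² / 4) = .1197.

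These are close to the printed .08 and .12, so that scale is a plausible source and no shortfall is claimed for counselling. It is an inference; the documents do not confirm it.

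**2. The ban at campus level.** Design effect DE = 1 + (m − 1)·ICC = 1 + 33.4·ICC. SE = √(4·DE/550) in SD units. Noncentral t on 14 df.

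| Assumed ICC | DE | Effective N | Ban detectable effect, 14 df (SD) | Same SE, 546 df (SD) | Ban on four-cell scale | Ban power at 0.239 SD |
|---|---|---|---|---|---|---|
| 0 | 1.00 | 550 | 0.257 | 0.239 | .091 | 74% |
| .01 | 1.33 | 412 | 0.297 | 0.276 | .105 | 62% |
| .02 | 1.67 | 330 | 0.332 | 0.309 | .117 | 53% |
| .05 | 2.67 | 206 | 0.420 | 0.391 | .148 | 36% |

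At ICC 0 the gap from counselling comes only from the 14 df. At any positive ICC it remains even if the ban is credited with 546 df. A simulation (16 campuses of 34, 20,000 runs) gave campus-level power of 73%, 62%, 53% and 36%. It also gave a type I error of .050, .091, .133 and .228 for an individual-level test of the ban, so 0.239 SD is not a valid figure for the ban once ICC exceeds 0.

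**3. What .08 would mean for the ban.** Power on 14 df:

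| Reading of .08 | Effect in SD | ICC 0 | .01 | .02 | .05 |
|---|---|---|---|---|---|
| d | 0.08 | 14% | 12% | 10% | 8% |
| Cohen's f | 0.16 | 42% | 33% | 27% | 19% |
| Four-cell scale | 0.226 | 69% | 57% | 48% | 33% |
| f² | 0.566 | >99% | >99% | >99% | 96% |
| eta² | 0.590 | >99% | >99% | >99% | 98% |

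Under f² or eta² the ban keeps 80% power up to an ICC of about .115 or .128. But .08 would then not be the smallest detectable effect (about .014 for counselling), and an interaction of .12 would be a difference-in-differences of 1.39 or 1.48 SD, far above the detectable 0.48 SD.

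**4. Covariate adjustment needed to bring the ban to 0.239 SD.** If variance is removed equally at both levels, the share is 1 − (0.239/detectable effect)²: about 35%, 48% and 67% at ICC .01, .02 and .05. If covariates absorbed all between-campus variance, the ban's figure would be 0.250 to 0.257 SD, and about 13% of total variance in all would have to go. Adjustment that removes within-campus variance also lowers counselling's figure.

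**The case against.** The strongest reply is that the calculation matches the analysis as written. The planned ANOVA and regression work at the individual level, and on the four-cell scale the printed figures come out, so what is missing is an assumption rather than a correct sum. That is fair to the arithmetic. It does not make the figure valid for the ban, because an individual-level test of a campus-randomised factor is anti-conservative at any positive ICC.

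Second, the relevant ICC is the residual one, after baseline value, BMI, intake, race/ethnicity and sex, and after design stratification ("Affiliates will be stratified by their location (urban vs. rural) and number of employees"). If those terms took up most of the between-campus variance, the gap would shrink towards 0.26 v 0.24 SD. This stands as a limit on size: the 36% figure belongs to the top of the assumed range. But the plan credits no such gain and gives no figure for it.

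Third, repeated measurement may help. Waist is measured at 6 months, so it could gain something. HOMA could not: "We will collect blood samples in the workplace labs at baseline and 12 months".

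Fourth, the mixed-model provision could be said to cover clustering. The exploratory model is named for the brief intervention. The contingent sentence could reach the ban, but neither enters the power calculation.

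Finally, SD units alone do not give centimetres of waist or HOMA units, because the documents state no outcome SD. That is correct, and the fix allows for it.

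**Conclusion.** The point holds. The single .08 cannot describe both interventions. Under a valid campus-level test the ban's smallest detectable effect is larger than counselling's: 0.26 to 0.42 SD against about 0.24 SD over assumed ICCs of 0 to .05.

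This rests on N = 550, equal campus sizes, a two-sided .05 test, 14 df and no credited covariate gain. The direction holds at every positive ICC; the size depends on a residual ICC that the documents do not give. Whether the ban falls short of the printed .08 depends on the unnamed scale: it does under d, Cohen's f or the four-cell scale, and does not under f² or eta² until the ICC passes about .115 or .128. It should be fixed, but it does not call the design into question.

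**What to change.** With N unchanged:

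- Name the effect-size scale and give the inputs used in the package.
- Restate detectable effects in SD units, separately: counselling about 0.24 SD; interaction f = .12, a difference-in-differences of about 0.48 SD before any campus-by-counselling variation; ban from 16 campuses and 14 df over an ICC range labelled as an assumption (for example 0 to .05, giving 0.26 to 0.42 SD). Say whether the ICC is raw or residual.
- Convert to centimetres and HOMA units with a stated outcome SD. The pilot described in Section 2 collected both measures and could supply one.
- Credit covariates, stratification or repeated measures only with their assumed size stated. The earlier 8-campus Sutter trial (Section 2) could supply an ICC for SSB consumption, but not for the primary outcomes: its anthropometrics were interrupted and it had no serum biomarkers.
- Qualify the fully powered claim in Section 3 to match.
- Tidy-up with no material effect: 80% of 700 is 560, not 550.

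The cost is a recalculation and some wording, with no extra participants. The stated sensitivity for the ban becomes less favourable. Whether the main models should carry a campus term is a separate decision that this change does not settle, but the ban's power figure and its primary test should end up on the same basis.

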Online Data Collection Evaluating UCSF Sales Ban: Observational data from an online survey of 2556 UCSF employees suggests that higher-risk demographic groups could disproportionately respond to the proposed intervention. Sample retention in this online study was 89% at the 12-month follow-up. Ethnic minority employees were twice more likely to report heavy consumption at baseline. Latinos experienced a more pronounced decline following the sales ban than Whites (by -3.7oz/day, $p < .007$). The lowest occupation stratum (service/manual workers) experienced a 30% reduction in consumption compared to 13% in the highest occupational group (academic medicine faculty) ($p < .0001$). *While limited by an observational approach, this study supports our proposed analyses by ethnic minority and lower occupational status, and speaks to our capacity for online data collection with good retention.*

Pilot Study of SSB Craving as a Mechanism: A published analysis of the UCSF pilot data found variable responses to the interventions for those with stronger SSB cravings (+1 SD above sample mean at baseline).¹² Individuals with weaker (-1 SD) SSB cravings reduced their SSB consumption, on average, by 12.8 oz/day ($p = .02$) more than individuals with stronger SSB cravings. However, among those with stronger cravings, those randomized to the multilevel intervention had significantly greater reductions in daily consumption (-19.21 oz/day vs. -2.49 oz/day, $p < .001$), a difference of 16.72 oz/day. *This study informs analyses proposed under Aim 3 by suggesting that employees with stronger SSB cravings may need the added motivational boost of brief counseling to achieve benefits on a par with others.*

Current Controlled Trial of Workplace Sales Ban in Sutter Health: In partnership with Sutter Health, we are currently completing a fully powered controlled trial of workplace SSB sales bans across 8 hospital campuses (5 intervention sites and 3 controls, $N = 657$ employees), funded by the [name] and John Arnold Foundation. Retention was 88% at 6 months and 78% at 12 (during the COVID-19 pandemic). Collection of anthropometrics for this controlled trial was interrupted by the pandemic, but we continue to collect dietary assessments and other data using an online format. At 6-months post-sales ban, there is a

**SUTTER HEALTH
INSTITUTIONAL REVIEW BOARD**

Protocol Summary Form

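### Biased attrition is tested for but not handled: no missing-data method is named, and 6-month values of people missing at 12 months have no stated use

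*Combined protocol and SAP*

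**What the plan says.** All references are to the combined protocol and SAP.

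- **Response to attrition** (4c, Aim 1, Anticipated Problems and Alternative Approaches). Biased attrition is named as a potential problem. The answers are a sample-size allowance of up to 20%, email and phone outreach, and a diagnostic: "We will conduct statistical tests to determine if attrition is biased on baseline risk levels", demographic factors including region, or study condition. No action is tied to the result. Aim 2 says attrition is handled as in Aim 1, and Aim 3 repeats the caveat.
- **Data used** (4c, Aim 1, Analytic Plan): "We will analyze Aim 1 using all data collected at the baseline, 6- and 12-month time points".
- **Methods** (same place): "First, we will use ANOVA to compare group means", then a linear regression. The worked example models HOMA change on the two assignments, baseline HOMA, baseline SSB intake, baseline BMI, race/ethnicity and sex. The same procedure is to be repeated for every other outcome. Aim 2 adds the interaction.
- **Mixed models.** In Aim 1 the only one is exploratory and nests people within sites, not visits within people. Aim 3 uses mixed models for the craving texts, as part of an exploratory mediation analysis.
- **Visits** (4b, procedures table). Waist, weight, BevQ and ASA24 are scheduled at baseline, 6 and 12 months. Blood, and therefore HOMA, is scheduled at baseline and 12 months only.
- **Prior retention** (section 2, current controlled trial in Sutter Health): "Retention was 88% at 6 months and 78% at 12", during the pandemic.

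**The concern.** A test for biased attrition does not deal with it. A non-significant result does not show that the losses are harmless, and the plan does not say what a significant result would change. The listed tests also look only at baseline characteristics and study condition. They do not ask whether people with a poor 6-month response were more likely to leave, which is the mechanism most likely to distort a 12-month comparison between arms.

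The stated methods take one follow-up quantity per person. Someone with a 6-month waist, weight and beverage record but no 12-month visit has no 12-month change to enter. If poor early responders leave more often in an intervention arm than in its comparator, those who remain make the intervention look better than it is. The 6-month values that could reduce this bias would already be in the database. Leaving the choice open also means that the missing-data method would be picked after the pattern of loss is known.

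**Working it through.** **Inputs from the documents.** Enrolment: "With an initial N of 700 drawn from 16 Sutter Health sites randomly assigned to the sales ban and control conditions". Retention: "Calculations are conservative, based on 80% retention of participants after 12 months". Resulting N: "80% retention would result in an overall N of 550 at 12 months" and "This results in approximately 138 in each of four experimental conditions". Prior Sutter retention is 88% and 78%. **Input not in the documents:** the correlation r between 6- and 12-month values given baseline, taken here as 0.5 to 0.8.

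**Step 1: the plan's own figure.** 700 × 0.80 = 560. The plan states 550, which is 550/700 = 78.6% retention; 550/4 = 137.5, or about 138 per condition. The difference of 10 is immaterial here. What matters is that power is set on the people expected at 12 months, which fits a complete-case analysis. The 20% allowance is called conservative, yet the Sutter trial lost 22%, although under pandemic conditions.

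**Step 2: who has 6-month but not 12-month data.**
- Present at 6 months: 700 × 0.88 = 616.
- Present at 12 months: 700 × 0.78 = 546.
- Missing at 12 months: 700 − 546 = 154.
- If dropout is monotone, 616 − 546 = 70 have 6-month data only, which is 70/154 = 45% of those missing. The other 84 have baseline data only.
- At the planned 80% retention the figure is 616 − 560 = 56.

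**Step 3: precision gained by using the 70.** Under monotone dropout, the variance of a 12-month mean is proportional to r²/616 + (1 − r²)/546. Effective N is its inverse.

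| r (given baseline) | Effective N | Gain over 546 |
|---|---|---|
| 0.5 | 562 | 2.9% |
| 0.7 | 578 | 5.9% |
| 0.8 | 589 | 7.9% |

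If the raw correlation ρ is the same between all pairs of visits, then r = ρ/(1 + ρ). In that case ρ from 0.5 to 0.95 gives r from 0.33 to 0.49 and an effective N of only 553 to 561. These figures ignore clustering by campus. They apply to waist, weight/BMI and SSB intake. HOMA has no 6-month value of its own, so they do not apply to it.

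**Step 4: possible size of bias (hypothetical).** Within an arm, the completer mean minus the full mean equals the dropout fraction times the completer–dropout gap. The gaps below are assumed, in SD units after baseline adjustment.
- 22% dropout in both arms, same gap in both: bias 0.
- 27% v 17% dropout, gap of 0.25 to 0.5 SD in both arms: 0.10 × 0.25 = 0.025 to 0.10 × 0.5 = 0.05 SD.
- 22% dropout in both arms, gap of 0.25 to 0.5 SD in one arm only: 0.22 × 0.25 = 0.055 to 0.22 × 0.5 = 0.11 SD.

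For scale, the smallest main effect detectable with 80% power at two-sided 0.05 and N = 550, ignoring clustering, is 2.80 × √(2/275) = 0.24 SD.

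**The case against.** A reader might infer that the plan discards the 6-month data, analyses completers only, and leaves attrition bias wholly uncorrected. The documents do not support that.

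- **Discarding is not stated.** The Aim 1 analytic plan says the opposite, that data from all three visits are used. No analysis set is defined, the type of ANOVA is not given, and the change window for waist or SSB intake is not fixed. The worked example is HOMA, which can only be a single change. What stands is that no named method delivers the stated intention. Even a classical repeated-measures ANOVA drops anyone with a missing visit.
- **Some bias is dealt with.** If dropout depends only on assignment and the baseline covariates in the regression, and that model is correct, complete-case regression is valid. This protection does not extend to dropout driven by response after randomisation.
- **Tests are not the only response.** Outreach and the sample-size allowance are real measures. They limit the amount of loss or protect power, but neither corrects an estimate.
- **The 6-month argument does not reach HOMA directly.** This stands in full for one of the two primary outcomes. Any recovery there depends on how well 6-month waist, weight and SSB intake predict 12-month HOMA, and the documents give no figure for that.
- **The numbers are modest or assumed.** The precision gain is at most about 8%. The bias figures rest on invented gaps and can be zero. The case therefore rests on the missing specification, not on a demonstrated bias.
- **The remedy is one of several acceptable packages, and describing who was lost remains useful.** This is accepted; the attrition tests need not be removed.

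**Conclusion.** The point holds in this form: the plan's only analytic response to biased attrition is a set of tests with no stated consequence. It specifies no missing-data method or sensitivity analysis and does not say how 6-month data from people missing at 12 months would be used. Followed as written, the methods give a complete-case 12-month comparison by default, with about a fifth of participants absent.

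About 70 of 700 people are affected if the Sutter retention recurs and dropout is monotone. The precision at stake is small: effective N rises from 546 to about 562–589 if the correlation given baseline is 0.5–0.8, and by less under lower correlations, for waist, weight/BMI and SSB intake only. The stronger reason to act is protection against dropout related to early response. The size and direction of that bias cannot be known from the documents. The plan should be changed, but this does not undermine the design.

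**What to change.** Amend section 4c as follows.

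1. Name the 12-month contrast as primary for each primary outcome.
2. For waist, weight/BMI and SSB intake, fit one longitudinal mixed model to the baseline, 6- and 12-month values of all randomised participants, with visit by sales ban by counselling terms and person and campus effects. Individual randomisation follows completion of the baseline measurements, so every participant randomised to counselling or control should contribute.
3. For HOMA, use multiple imputation by arm, with baseline HOMA and 6-month weight, waist and SSB intake as auxiliary variables.
4. Keep the description of attrition, and report it also by 6-month response. Do not let a significance test decide which analysis is used.
5. Add a delta-adjusted sensitivity analysis that shifts the unobserved 12-month values by arm over a stated range and shows where the conclusion changes. This matters most for HOMA and for those lost before 6 months (84 in the illustration), for whom only baseline data exist.

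The cost is analysis-plan wording and modest programming, with no new data. The drawback is that the mixed model and the imputation both assume data are missing at random; item 5 probes that assumption.
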